
Rationale:

The HPV E6/E7 oncoproteins have significant roles in malignant transformation and are consistently expressed in malignant cervical tissue. Increasing levels of E6 and E7 expression cause genetic instability, and implies a risk for cellular changes, which results in a selective growth advantage (31, 34-37). The APTIMA® HPV Assay that we will be utilizing in our studies detects full-length HPV E6/E7 mRNA for HPV types 16, 18, 31, 33, 35, 39, 45, 51, 52, 56, 58, 59, 66, and 68 and correlates very well with integrated HPV, which in turn correlates with full-length HPV E6/E7 protein levels (38).

All methodologies for evaluating the expression and function of HPV E6/E7 are ongoing in the laboratory of the co-investigator ([name]) and are described in referenced publications (27-34). The expression of HPV E6/E7 proteins will be assessed by the APTIMA* HPV Assay using liquid-based cytology specimens.

Specific Aim 2 (Secondary Objective):

To quantify levels of curcumin in the cervix of women in the curcumin treatment arm.

Rationale:

To date, there are no published data on the tissue penetration of curcumin in vivo. This will establish the level of curcumin penetration in cervical tissue as well as the cumulative effect of weekly curcumin over time. This study will establish the baseline which is crucial in designing further curcumin intervention studies. The methodology of curcumin measurement for this study is well documented in Subhashini et al (16).

Specific Aim 3 (Exploratory Aim):

To determine the association between curcumin and other known biomarkers of cervical disease and its effect on the vaginal microbiome.

Rationale:

To determine the most relevant duration for curcumin treatment, as well as identify additional biomarkers that are regulated with the pharmacological activity of curcumin, we will measure mRNAand/or protein expression levels of p16INK4a, p53, Rb, VEGF and NF-κB in cervical biopsy specimens. A combination of immuno-histochemical methods and other molecular assays (RT-PCR, ELISA, TransAM NF-κB DNA binding ELISA) to determine mRNA levels and protein levels on transcription factor binding activity will also be done.

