We are proposing a prospective, randomized, two-arm, open label pilot study to demonstrate the in vivo effects previously seen in preclinical studies using cervical cancer cell lines16-20. Study participants will be recruited from the Grady Cancer Center of Excellence and the Infectious Disease Program at Grady's Ponce Clinic. A convenience sample of 40 HIV uninfected and infected participants with biopsy-proven HSIL will be randomized to one of two arms (2000 mg of curcumin powder in capsules or placebo inserted intravaginally weekly at bedtime for 12 weeks, (excluding the time when they are on their menses) as demonstrated in the schema.

Cervical cytology, vaginal swabs, colposcopies and biopsies will be performed every 4 weeks during each study visit for the study duration for the primary objectives outlined in specific aims 1-3. These time points were selected to acquire cervical samples prior to treatment, during treatment and 4 weeks after treatment completion (LEEP specimen). Study drug and placebo will be administered during weeks 1-12 (12 weeks of treatment) and no treatment will be administered during weeks 13-16 (washout period). Cervical biopsies will be performed in areas with a colposcopic suggestion of HSIL disease and four additional cervical punch biopsies (one specimen from each of four quadrants) of the cervix will be done for downstream biomarker analysis. The laboratory, pathology and data analysis staff will be blinded to treatment arm. The clinicians performing the colposcopies nor the participants will not be blinded secondary to the evident color of curcumin.

Study Population

HIV uninfected and infected women will be recruited for this study. We will focus only on HIV infected women without an AIDS defining disease, given that the risk of progression from high grade lesions to invasive carcinoma is faster in HIV infected subjects who are significantly immune compromised.

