All study subjects will be instructed to insert 2000 mg total curcumin capsules at bedtime every week. The study subject will place four 500 mg Curcumin C3 Complex® capsules into the opening of the vaginal applicator and insert the capsules using the applicator while lying on their back with their knees bent (Figure 1). The subject will be instructed to gently inserted the capsules into the vagina as far as it will go

comfortably (Figure 1), similar to a tampon insertion or other common intravaginal drugs (fungal treatments). All required capsules should be inserted at one time. After successful insertion of the capsules, the subject will remove the vaginal applicator for disposal. The study subject who is randomized to the gelatin capsules will insert the placebo capsules in the same manner as the study drug. [name] holds the FDA IND (no.103,496) for the intravaginal use of curcumin for human clinical trials.

Figure 1. Insertion of study drug

Dosing regimen

2000 mg total (4 capsules) of curcumin powder in capsules or placebo inserted intra-vaginally weekly at bedtime for 12 weeks, (excluding the time when they are on their menses).

Treatment Plan

There is no concern about progression of cervical intraepithelial lesion (CIN) 3 disease or severe dysplasia within the time course of this study (4-5 months) based on the natural history of CIN 3 (severe cervical dysplasia). Approximately 30% will regress and 50-70% will progress to cancer however the rate of progression to cancer takes 5-10 years to occur. Though the data of the natural history of cervical dysplasia was in HIV uninfected women; data from the Women Interagency HIV study has also reported that in a well followed cohort of HIV infected women, rates of invasive cervical cancer was the same in HIV infected women as in HIV uninfected women. We expect the same outcomes in both cohorts of women.

In addition time, course to cancer is not significantly faster to require treatment to occur sooner than their HIV negative counterpart. Presently, HIV positive young women with histologic HSIL disease (CIN 2,3) are now offered in clinical practice active monitoring with colposcopies every 6 months instead of treatment of cervical dysplasia to avoid the negative pregnancy outcomes from treatment. This change in practice is due to the number of HIV positive women desiring fertility and pregnancy and the effectiveness of HAART in pregnancy.

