| Targeted cervical biopsies | | * | * | * | * |
| 30 day supply of medication (curcumin/placebo) | | * | * | | |
| Pill diary review | | | * | * | * |
| Partner notification letter (distribution) | * | | | | |
| Leep Procedure | | | | | * |

All subjects will be asked to complete an acceptability questionnaire at the end of the study. Focus group: 20 subjects will be invited to attend a focus group to discuss the acceptability of the medication. *HIV test will not be performed if there is a negative test documented in the medical records 3 months prior to screening visit.

SCHEDULE OF EVENTS

Screening Visit

Screening evaluations will determine eligibility and will occur prior to the participants' enrollment into the study. At the screening visit subjects will have:

- A urine test to see if they are pregnant.
- HIV status will be confirmed based on medical records or testing during the screening visit
- They will be asked to agree to the use of reliable birth control: Combined oral contraceptive pill (OCP), Long Lasting Reversible Contraceptive (LARCP), Bi-Lateral Tubal Ligation (BLT) and Depo-Provera Shot/Birth control shot.
- They will be given a partner notification letter about the study.
- A full physical exam will be done.
- A colposcopy with Pap smear to check for the presence of human papilloma virus; vaginal sampling for infection and microbiome to get a baseline state of the vagina.

Study Visits

Baseline and all other study visits will occur after the screening visit.

Baseline:

- Urine test to see if they are pregnant.
- A pelvic exam will be done.
- Vaginal sampling and colposcopy with targeted cervical biopsies will be done.
- They will be given a pill diary and a 4-week supply of the study medication (curcumin or placebo).
- Instruction on insertion of the intravaginal capsules will be given and they will be reminded of potential side effects of the medication.
- They will be asked to return for another study visit 4 weeks later.

Study visits wk 4 and wk 8:

- Urine test to see if they are pregnant.
- A pelvic exam.
- Vaginal sampling and colposcopy with targeted cervical biopsies.
- Their pill diary will be reviewed (aspects of time, frequency and date of distribution of the medication)
- They will be given another 4-week supply of the study medication (curcumin or placebo).
- They will receive a phone call twice a week to address any issues.
- They will be asked to return for another study visit 4 weeks later.

Study visits wk 12:

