- Primary endpoints: Human papillomavirus E6/E7 (HPV E6/E7)
- Secondary endpoints: NF-κB, p16INK4a, Rb, p53 and VEGF.

HPV E6/E7 mRNA testing has been demonstrated to be a useful tool in the diagnosis of cervical cancer prevention and will be the primary end-point for this aim. The primary objective for this study is to look at the association between curcumin and cervical disease. In vitro work shows that curcumin treatment inhibits the transcription of HPV E6/E7, thus restoring the expression of proteins such as p53 and that over expression of HPV E6/E7 is a good indicator of risk and progression to cancer. (Maher DM, 2011 Jan;50(1)). Collectively the vitro and our in vivo findings may show that curcumin should be considered an effective chemopreventive and therapeutic agent for cervical cancer prevention and treatment.

Aim2: To quantify levels of curcumin in the cervix of women in the curcumin treatment arm. The mean tissue concentration of curcumin in the cervix at each time point (baseline, 1,2,3,4, and 5 months) will be calculated. This secondary objective quantifies the pharmacologically active levels of curcumin recovered from cervical tissue, for information to be gathered on the levels of curcumin that is absorbed into the cervical tissue and thus eliciting a direct pharmacological effect.

Aim 3: To determine the association between curcumin and other known biomarkers of cervical disease. This exploratory aim seeks to use repeated-measures analyses, utilizing a linear mixed model for the curcumin group to assess the association between and each biomarker (NF-kB, p16INK4a, Rb, p53 and VEGF) and the concentration of curcumin at each time point (baseline, 1, 2, 3, 4, and 5 months).

The primary analysis will be conducted with a two sample two sided t-test to compare the each of the primary endpoints and secondary endpoints, between the two arms of the study, those on treatment (curcumin capsules) and those on the placebo, respectively. If normality cannot be assumed a Wilcoxon rank-sum test will be used instead. Chi-square test or Fisher's exact test will be used to compare categorical characteristics by treatment group.

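### Aim 2 reports tissue curcumin only as a mean per nominal month, with no account of days since the weekly dose, so level and spread mix penetration with timing

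*Combined protocol and SAP*

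**What the plan says.** Under Study Drug Administration, participants are to "insert 2000 mg total curcumin capsules at bedtime every week". The Dosing regimen section has the capsules "inserted intra-vaginally weekly at bedtime for 12 weeks, (excluding the time when they are on their menses"). Neither section names a weekday or ties the dose to the visit day. Neither says whether a dose that falls in menses is skipped or moved.

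On sampling, Research Design and Methods places biopsies at every 4-weekly visit and explains: "These time points were selected to acquire cervical samples prior to treatment, during treatment and 4 weeks after treatment completion (LEEP specimen"). The lists for the baseline, week 4, week 8 and week 12 visits each end the same way: "They will be asked to return for another study visit 4 weeks later". The only gap from treatment that is given a length is the 4-week washout before the LEEP.

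On analysis, Aim 2 in the Statistical Analysis section plans one summary: "The mean tissue concentration of curcumin in the cervix at each time point". It adds: "This secondary objective quantifies the pharmacologically active levels of curcumin recovered from cervical tissue". The rationale under Specific Aim 2 sets the purpose: "This will establish the level of curcumin penetration in cervical tissue as well as the cumulative effect of weekly curcumin over time", followed by "This study will establish the baseline which is crucial in designing further curcumin intervention studies".

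The pill diary is reviewed at visits, including for time and date, but Assessment of Compliance gives it one stated use, a count of nights of use. Neither the Aim 2 summary nor the Aim 3 concentration model mentions time since dose.

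**The concern.** A tissue concentration is hard to interpret without knowing how long after the dose it was taken. With a weekly dose on a free night, two equally compliant women at the week 4 visit may be a day and a week past their last insertion. Averaging them gives a figure that depends on the mix of intervals as well as on how much curcumin enters and stays in the cervix. A low mean could then indicate poor penetration or late sampling. A wide spread could be real variation between women or variation in dose night.

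Aim 2 is the secondary objective and its output is purely descriptive, so the interpretability of these levels is what it has to offer. The protocol also says that no in vivo tissue penetration data have been published, so a later trial could not easily correct the figures for timing from another source.

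**Working it through.** **The plan's own figure.** Aim 2 has no design figure. The only one in the document is the E6/E7 power: 20 per arm, ratio 1.536, coefficient of variation (CV) 0.5, two-sided 0.05. On the log scale the SD is √ln(1 + 0.5²) = 0.4724 and the difference is ln 1.536 = 0.4292. The noncentral t with 38 df gives 79.95%, which matches the stated 80% after rounding. It uses no curcumin level, so this point leaves it unchanged.

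**Inputs from the document.** One dose a week, 12 weeks of dosing, biopsies at weeks 4, 8 and 12, and 20 women in the curcumin arm.

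**Assumptions not in the document.** First-order loss from tissue; the same kinetics in every woman; no missed dose; last dose equally likely 1, 2, …, 7 days before the biopsy; tissue half-life h of 1, 3 or 7 days.

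**Step 1: level and spread at one visit.** The level d days after a dose is proportional to 2^(−d/h). Earlier weekly doses multiply it by a factor that does not depend on d, so ratios between days are unchanged by accumulation.

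| | h = 1 day | h = 3 days | h = 7 days |
|---|---|---|---|
| Day 1 / day 7 = 2^(6/h) | 64 | 4.0 | 1.8 |
| CV from timing alone, days 1–7 | 1.17 | 0.45 | 0.20 |
| Same, as standard error of a mean of 20 (CV/√20) | 26% | 10% | 4.4% |

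If a dose due in menses is skipped rather than moved, the interval lengthens by a further 7 days.

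**Step 2: trend from week 4 to week 12.** With r = 2^(−7/h), true build-up from 4 to 12 doses at a fixed interval is (1 − r¹²)/(1 − r⁴) = 1.000, 1.002 or 1.066 for h = 1, 3 or 7 days.

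Visits are 28 days apart, which is 4 × 7. A woman who keeps one dose night and a 4-week visit cycle therefore has the same interval at weeks 4, 8 and 12, and timing cancels from her change. If she starts each supply on the visit night, that interval is 7 days every time.

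The trend is disturbed only if intervals move. A 1-day shift in one woman's interval changes her level by 2^(1/h) = 2.0-, 1.26- or 1.10-fold. The table gives the simulated 95% range of the week 12 / week 4 ratio of means (20 women, 20,000 runs, timing the only source of variation):

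| Intervals at the two visits | h = 1 | h = 3 | h = 7 |
|---|---|---|---|
| Constant within each woman | 1.000 | 1.002 | 1.066 |
| 7 days, each moved by −1, 0 or +1 day | 0.72–1.41 | 0.89–1.12 | 1.01–1.12 |
| Drawn afresh from 1–7 days | 0.46–2.14 | 0.76–1.32 | 0.94–1.20 |

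**The case against.** A reader might infer from the last row of the second table that Aim 2 cannot separate build-up from timing at all. The document does not support that. The row needs each woman's interval to be redrawn at every visit, whereas weekly dosing and 4-weekly visits, followed regularly, hold it constant. Only drifting dose nights, moved visits or menses would disturb the trend. Fixing the timing would not make build-up easy to see either: under the same model the true rise is 6.6% at most, which is small for 20 women.

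It might also be inferred that a fixed dose-to-biopsy interval is needed. That is closer to a design preference. Sampling across the dosing week, with dates recorded, can show something of how the level decays, which a single fixed day cannot.

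Three further objections have weight:

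- The size rests on a half-life that nobody has stated; at 7 days the effect is modest.
- The diary review already covers time and date and there are twice-weekly calls, so the information is probably being collected.
- The schema, the diary form and any participant dosing instructions are not visible and might set a dose day.

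What remains is that the analysis text makes no use of time since dose, and a constant interval within each woman does not make it the same across women. The absolute level and the between-woman spread stay mixed with timing.

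**Conclusion.** The point holds as a reporting gap for the on-treatment samples at weeks 4, 8 and 12. A monthly mean alone cannot be read as a penetration level when compliant women may be anywhere from about 1 to 7 days past a dose. Timing alone would produce a 64-fold to 1.8-fold difference across the week for assumed half-lives of 1 to 7 days. The direction does not depend on the half-life; the size does. The effect on the week 4 to week 12 trend is conditional on intervals shifting within women.

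Baseline (before any dose), the week 16 LEEP (after a stated washout) and the between-arm E6/E7 comparison are not affected. Because the schema is not shown, the absence of a set interval is a statement about the visible text only. The severity is low: a cheap improvement that the sponsor could make.

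**What to change.** For each week 4, 8 and 12 biopsy, take the date of the last dose from the pill diary. Derive two variables: days since last dose and cumulative doses taken. Report Aim 2 concentrations by both, as a plot or table for the curcumin arm, alongside the planned monthly means.

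Optionally, ask each woman to keep the same dose night relative to her visits, which protects the trend at no analytic cost.

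In Aim 3, use the two variables descriptively or in a sensitivity analysis only. They are causes of the concentration that serves as predictor there, so making them required covariates would remove part of the variation the model is meant to use.

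The cost is two derived variables and a little more analysis work. No visit or sample is added.

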Cervical cancer is the third most common cancer worldwide. The causative agent responsible for cervical cancer is the persistent infection with oncogenic Human Papillomavirus (HPV). Rates of cervical cancer and HPV infection are increased particularly in HIV-infected women due to immunosuppression and cervical cancer is an AIDS-defining diagnosis. Despite the promise of HPV vaccine in the prevention of cervical cancer, the widespread availability of this vaccine is limited due to cost and accessibility. Therefore, prevention strategies to reduce cervical cancer after HPV exposure entail treatment at the most severe premalignant state (high grade squamous intraepithelial lesion or HSIL). Unfortunately, this procedure is expensive and not widely available in resource-limited areas. There is a desperate need for an inexpensive, non-invasive alternative method to treat these premalignant cervical lesions.

Curcumin, an extract from turmeric, a popular culinary spice, has been used in traditional Indian medicine for its anti- inflammatory and anti-infectious properties. Recent studies have shown the potential effect of curcumin to reduce tumors and precancerous lesions in animal and human cancer cells. It is postulated that curcumin achieves its effect on cancer cells by modulating different cellular pathways as well as altering HPV effect on tissue cells.

The purpose of this study is to see if curcumin can reverse a cervical precancerous state by looking at people who have the condition and intervening with a study drug or placebo (an inactive drug), prior to planned therapeutic LEEP which is a treatment procedure for removing cervical cancer.

We plan to explore the effect of curcumin as a potential medical treatment in HIV uninfected and infected women with HSIL lesions of the cervix. 40 women with HSIL of the cervix will be enrolled to either insert 2000 mg capsule of curcumin in their vagina weekly or placebo. They will have regular monthly visits for the 4 months and then undergo removal of the precancerous cells as recommended standard of care.

SUMMARY

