Enrolled subjects will be asked to agree to the use of reliable birth control: Combined oral contraceptive pill (OCP), Long Lasting Reversible Contraceptive (LARCP), Bi-Lateral Tubal Ligation (BLT) and Depo-Provera Shot/Birth control shot and they will be given a partner notification letter advising them to use a condom when having vaginal sex with their partner and the risks associated with lack of use of a condom.

Clinical care practice guidelines indicate colposcopy every 6 months. We will be following these subjects every month with colposcopy for research purposes of this study, which is more than sufficient to clinically monitor and capture any women at risk for progression of disease. Subjects will be informed that the alternative to this study or if disease progression occurs, is referral for continued clinical care with their provider where they will this they will discuss the treatment (Leep with continued active monitoring-colposcopy with biospies) with their provider at the Grady Cancer Center of Excellence treatment Clinic or at the Emory Clinic.

Randomization Method

The treatment assignments will be generated with the use of a pseudo-random-number generator with randomly permutated blocks that will be used to ensure balance between the number of subjects assigned to each treatment (1st: 2000 mg of curcumin for 12 weeks versus placebo capsules for 12 weeks). Before the study starts, the Pharmacist at Ponce Clinic (IDP) or Grady CRN will be sent a batch of sealed, sequenced, opaque envelopes containing the treatment assignment. The envelopes will have a unique ID consisting of a sequence number determining the treatment arm. Once informed consent is obtained on a subject, the Study Coordinator/P.I. will set up an appointment for the screening visit at the Ponce clinic (IDP) or Grady CRN to confirm clinical eligibility. Once the participant is cleared to enter the study, they will be given a unique ID associated to the batch of envelopes in the care of the Grady CRN or Ponce Clinic (IDP) Pharmacist.

Subject Recruitment:

All subjects will be recruited from Grady Cancer Center of Excellence at Grady Memorial Hospital (GMH) and the Grady Infectious Disease clinic at Ponce (IDP) per the inclusion and the exclusion criteria below.

Inclusion Criteria:

- 1. Age 21 years and older
- 2. HIV uninfected and infected women (without AIDS defining illness)
- 3. HSIL cytology with no invasive features identified on colposcopy or the baseline biopsy

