Acceptability Questionnaires: Descriptive statistics on subject and partner responses from the acceptability questionnaires will be reported.

Power and sample size calculation: The expression of E6/7 is the primary endpoint of the study and will be used in the power and sample size calculation with a two sample two sided t-test. In this study, we will enroll 20 patients in each of the two groups. Therefore, the group sample sizes of 20 in Curcumin group and 20 in placebo group will achieve at least 80% power at the significant level of 0.05 to detect a difference of a ratio of 1.536 or higher in the expression of E6/ between the two groups, assuming the coefficent of variation is 0.5.

SAFETY EVALUATION:

Adverse Events (AEs) and Serious Adverse Events (SAEs)

This investigational agent is studied under IND # 103496 and monitoring will be performed per previously agreed upon FDA guidance.

There may be some minor irritation from the intravaginal curcumin to the vaginal mucosa and staining of underwear. Other side effects which can happen include the upset stomach, diarrhea, burning sensation in the vagina, dizziness, insomnia, rash, pruritus generalized, and fever. The literature shows that over 13 subjects in United States and 151 subjects in India (10) have been studied with curcumin without any serious adverse effects.

Our phase I study has shown that curcumin is safe in dosage up to 2000mg.

Any patient intervention related adverse effects, an unanticipated problem, or reportable protocol deviation/ non-compliance will be reported to the Emory IRB office according to IRB P & P and to the FDA according to regulations.

Any serious adverse effects will be communicated by the principal investigator to the Emory IRB using the standard adverse event reporting forms.

SAEs will be defined per FDA standards and include those that result in death, are life threatening, result in a disability, cause for hospitalization, or to a congenital abnormality or birth effect. SAEs will be reported to the DSMC, IRB and FDA and manufacturer as required.

CLINCAL OUTCOMES AND MEASURES:

The table below gives the descriptions to be used to document findings during colposcopy.

| Colposcopic findings | | | | Presence | |
|----------------------|----------------------|----------------------|----------------------|----------|--------|
| | Grade 1 | Grade 2 | Grade 3 | | |
| | (Mild) | (Moderate) | (Severe) | Present | Absent |

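### HIV status and baseline E6/E7 are available before treatment, but neither the randomisation nor the unadjusted primary test uses them

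*Combined protocol and SAP*

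**What the plan says.** Under Research Design and Methods: "A convenience sample of 40 HIV uninfected and infected participants with biopsy-proven HSIL will be randomized to one of two arms". The number expected in each HIV group is not given. Under Randomization Method, the list uses "randomly permutated blocks that will be used to ensure balance between the number of subjects assigned to each treatment". No stratification factor is named, and no separate list is described for HIV status or clinic.

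Under Statistical Analysis: "The primary analysis will be conducted with a two sample two sided t-test", with the fallback "If normality cannot be assumed a Wilcoxon rank-sum test will be used instead". Neither test takes a covariate. Adjustment appears only in the secondary mixed models, where the covariates are not named.

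The Screening Visit section has HIV status settled from records or by testing before enrolment. The Schedule of Events has a Pap sample at screening and at baseline. The rationale for Aim 1 makes liquid-based cytology the assay specimen, and the secondary models list baseline as a time point. Both values will therefore be in hand.

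**The concern.** The documents themselves make HIV status the obvious candidate factor. The opening summary states: "Rates of cervical cancer and HPV infection are increased particularly in HIV-infected women due to immunosuppression". The primary endpoint is an HPV transcript, Aim 1 names both HIV groups, and HIV-infected women have their own eligibility rules.

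With 20 women per arm, blocks that balance only the arm totals leave the HIV mix to chance. If HIV status is related to E6/E7, an uneven split moves the observed ratio in that particular trial, and the t-test cannot take it out. An unadjusted test also leaves in the error term any variation that HIV status or the woman's own baseline value could explain. With planned power at 80% and no stated allowance for dropout, precision that is nearly free is worth taking.

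**Working it through.** **1. The plan's own figure.** The Power and sample size calculation gives "the group sample sizes of 20 in Curcumin group and 20 in placebo group", which "will achieve at least 80% power at the significant level of 0.05 to detect a difference of a ratio of 1.536 or higher", "assuming the coefficent of variation is 0.5".

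- Log-scale SD: σ = √ln(1 + 0.5²) = 0.4724.
- Effect: δ = ln(1.536) = 0.4292, so δ/σ = 0.9086.
- Noncentrality: λ = 0.9086 × √(20/2) = 2.873, with 38 df and two-sided 0.05.
- Power = 79.95%. The stated 80% is reproduced; exactly 80% needs a ratio of 1.5364.

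**2. Chance imbalance.** Let H of the 40 women be HIV infected. The number X in one arm is hypergeometric (40, H, 20), and the arms differ by |2X − H|.

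| H (share, assumed) | P(difference ≥ 4) | P(difference ≥ 6) |
|---|---|---|
| 8 (20%) | 23.5% | 4.4% |
| 12 (30%) | 30.1% | 8.2% |
| 20 (50%) | 34.3% | 11.3% |

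Simulated unstratified blocks of 4 (block size assumed) agree to within about 0.1 percentage point. The expected absolute difference is about 2.3-2.5 women for 30-50% infected.

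**3. Effect of an imbalance on the estimate.** Suppose HIV shifts log E6/E7 by h within-group SDs (assumed). A difference of m women multiplies the observed ratio by exp[(m/20) × h × σ_w], with σ_w = 0.4724/√(1 + p(1−p)h²) and p the infected share. At p = 0.5:

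- m = 4: 1.02, 1.05 and 1.09 for h = 0.25, 0.5 and 1.0.
- m = 6: 1.04, 1.07 and 1.14.

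The target ratio is 1.536.

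**4. Power with HIV in the model, arms balanced.** R² = p(1−p)h²/(1 + p(1−p)h²), λ_adj = 2.873/√(1−R²), 37 df. CV 0.5 is taken as the total variability.

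| h | R² (p = 30%, 50%) | Power (p = 30%, 50%) |
|---|---|---|
| 0 | 0, 0 | 79.9%, 79.9% |
| 0.25 | 1.3%, 1.5% | 80.4%, 80.5% |
| 0.5 | 5.0%, 5.9% | 81.9%, 82.2% |
| 1.0 | 17.4%, 20.0% | 86.8%, 87.9% |

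With no HIV effect the cost is one degree of freedom: 79.95% falls to 79.89%.

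**5. Power with HIV in the model, arms unbalanced.** Take 13 versus 7 with 20 of 40 infected. The arm-HIV correlation is 13/20 − 7/20 = 0.30, so the variance inflation is 1/(1 − 0.09) = 1.10.

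- h = 0: λ = 2.873 × √0.91 = 2.741, power 76.1%.
- h = 0.5: λ = 2.962 × √0.91 = 2.825, power 78.6%.

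**6. Baseline E6/E7.** With correlation r between baseline and outcome (assumed), λ = 2.873/√(1−r²). For r = 0.3, λ = 3.012 and power is about 83%. For r = 0.5, λ = 3.318 and power is about 90%.

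**7. Cost of unfilled blocks under stratification.** For the planned t-test, λ = 0.9086 × √(n₁n₂/40). Arms of 21/19 give 79.9% and arms of 22/18 give 79.6%.

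**The case against.** The strongest reply is that nothing in the documents shows HIV status to predict E6/E7 level among women who all have HSIL. The statements about higher rates concern who acquires HPV and cancer, and attribute this to immunosuppression. Eligibility limits that route: HIV-infected women need CD4 above 200, a sustained undetectable viral load and no AIDS-defining illness. The Treatment Plan also expects the same outcomes in both cohorts. This stands in large part. The Treatment Plan remark rests on cancer rates rather than transcript levels, but the HIV effect is unknown, and at 0.25 SD adjustment gains only about half a percentage point of power.

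A reader might infer that the design is biased or the test invalid. The documents do not support that. Randomisation protects the unadjusted comparison on average, and a six-woman difference is a tail event. A reader might also infer that adjustment is free in every case. It is not: with 13 versus 7 and no HIV effect, it lowers power to about 76%.

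The secondary mixed models do adjust for covariates and include baseline, so an imbalance could be examined there. They name no covariate, however, and leave the primary test unchanged. Envelopes held at two clinics would amount to partial stratification only if each had its own balanced sequence, which the text does not say; nor is clinic the same as HIV status. Finally, the study is called a pilot and concedes that small numbers limit inference from the repeated-measures models. It still claims a powered 0.05 test for its primary endpoint.

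**Conclusion.** The point holds as an inexpensive improvement, not as a defect in validity or sample size. Two pre-treatment values that the study already obtains are left out of the primary analysis, and one of them, known before allocation, is left out of the randomisation. A split differing by 4 or more HIV-infected women has about a 30-34% chance, and by 6 or more about 8-11%, if 30-50% of women are infected.

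The gain from HIV adjustment alone runs from nothing to about 8 percentage points of power (79.95% to 87.9%) over assumed shifts of 0 to 1.0 SD with balanced arms. The upper end needs an effect for which the documents offer no evidence. The baseline value is likely to bring more of the benefit, and it would absorb part of any stable HIV difference, so the two gains should not be added.

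These figures assume an HIV share, an HIV effect and a baseline correlation that the documents do not state. They also assume a quantitative E6/E7 readout analysed on the log scale, which the stated power figure fits, and that CV 0.5 describes all women together. If CV 0.5 instead describes variability within each HIV group, the planned test has about 78-79% power for an assumed HIV ratio of 1.25, or 73-75% for 1.5, and adjustment restores 79.9%.

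**What to change.** Pre-specify the primary analysis as a linear model of log E6/E7 on arm, baseline log E6/E7 and HIV status, and report the adjusted ratio with its 95% confidence interval. Keep the unadjusted t-test or Wilcoxon test as a sensitivity analysis. State this before any outcome data are seen by arm.

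If randomisation has not begun, also prepare two permuted-block envelope lists, one for HIV-infected and one for HIV-uninfected women. This makes the 13-versus-7 situation unlikely and with it most of the variance inflation. If randomisation is under way, make the analysis change only.

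The cost is one extra envelope list and one degree of freedom per covariate. There is some loss of precision if HIV turns out both imbalanced and unrelated to E6/E7, and the arms may finish at 21/19 or 22/18. No extra women, visits or samples are needed.
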